7.6. Spirometry Evaluations

The following parameters will be reported for each timepoint: FEV1 and FVC. The maximum of the measurements will be calculated. All measurements will be listed.

% Predicted Normal FEV1 = (Max FEV1/Predicted Normal FEV1)x100

% Predicted FVC = (Max FVC/Predicted Normal FVC)x100

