Repeat dose schedule to be followed for repeat dose cohorts in Parts 1 and 2 (other than Cohort A Part 1)

| Procedure | | | | | | | Trea | tment P | eriod, [| Days | | | | | | |
|---|----------------|------------|---|----|---|---|------|---------|----------|------|-----|----|-----|----------------|----|-----------------|
| | -1 | 1 | 2 | 3 | 4 | 5 | 6 | 7 | 8 | 9 | 10 | 11 | 12 | 13 | 14 | 15 |
| Inclusion and exclusion criteria | X | | | | | | | | | | | | | | | |
| Brief physical examination, oral examination | X | | | | | | | | | | | | | | | X |
| Substance testing (drugs, alcohol, tobacco1) | X | | | | | | | | | | | | | | | |
| Inhaler device training ² | X | | | | | | | | | | | | | | | |
| Serum pregnancy test in women | X | | | | | | | | | | | | | | | |
| Admittance to clinic | X | | | | | | | | | | | | | | ĺ | |
| Randomization | X ₃ | | | | | | | | | | | | | | 1 | |
| Discharge | | | | | | | | | | | | | | | ĺ | X4 |
| Dosing procedure training with bystanders | | X5 | | | | | | | | | | | | | 1 | |
| Haematology, clinical chem and urinalysis (include liver chem)6 | Х | | | | | | | Х | | | | | | | | Х |
| Spirometry | | X 7 | | Χ8 | | | χ8 | | | | | Χ8 | | | Х7 | |
| Telemetry (starting 30 min pre-morning dose and continuous at least 4h post-morning dose) | | Х | | | | | | Х | | | | | | X ⁹ | | |
| 12-lead ECG and vital signs ¹⁰ | XXX | Χ | | Χ | Χ | | Х | Х | Χ | | X11 | | X11 | | ĺ | |
| CCI15106-IP or placebo treatment BID, device incident assessment BID ¹² | | Х | Х | Х | Х | Х | Х | Х | Х | Х | Х | Х | Х | Х | Х | |
| PK blood sample ¹³ | | Χ | Х | | Χ | | Х | | Χ | | Х | | Х | | Х | X |
| BAL | | | | | | | | | | | X14 | | | | | |
| Urea blood sample | χ15 | | | | | | | | | | | | | | | |
| AE review | () | | | | | | | | | | | | | | | |
| SAE review | | | | | | | | | | | | | | | | |
| Concomitant medication review | (| | | | | | | | | | | | | | | > |

- 1. Tobacco test to be performed only in healthy participants
- 2. Day -1 inhaler training may be done on Day 1 instead, before the first dose administration. Other time-points may be added per investigators discretion.
- 3. Can be performed on Day 1 prior to dosing
- 4. After all procedures and assessments are complete
- 5. To be done only in Cohort(s) where bystanders are present. Can be performed on Day -1 instead, if desired. Other time-points may be added per investigators discretion.
- 6. To be drawn fasting (for at least 8 h)

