- 7. To be performed at the following timepoints in the mornings only: pre-dose, and 0.25 (in participants with COPD only), 0.5, 1, 4 h post-dose
- 8. To be performed at the following timepoints in the mornings only: pre-dose and 4 h post-dose

- 9. Telemetry may be performed on Days 11 or 12 instead, not to coincide with the BAL procedure.
- 10. ECG and vital signs to be obtained 2 h after the morning dose
- 11. When BAL is performed, vital signs and ECG will be performed before and after the procedure and oxygen saturation will be measured continuously.
- 12. For cohort with bystanders, BID doses may have ±1.5 h window.
- 13. PK samples on days 1 and 14 will be collected at the following timepoints: pre-dose, 0.25, 0.5, 0.75, 1, 2, 4, 6, 8, 10, 12 h. The evening dose will be given after 12 h post-dose sample is collected. On all other days, PK sample will be collected once, before the morning dose. When BAL is performed, one additional PK sample will be collected after dosing immediately prior to bronchoscopy
- 14. Done once during these four days, as soon as possible (within 1 h) after the first dose of the day
- 15. To be collected immediately before bronchoscopy

Schedule for Cohort C Part 1 (bystanders and air monitoring), to be executed concomitantly with Cohort B Part 1

| Procedure Treatment Period, Days | | | | | | | | | | | | | | | | |
|---|----------------|----------------|---|-----------------------|----|--------------------|-------------------|----------------|----|---|-----------------------|----|----|----|----------------|----|
| | -1 | 1 | 2 | 3 | 4 | 5 | 6 | 7 | 8 | 9 | 10 | 11 | 12 | 13 | 14 | 15 |
| Inclusion and exclusion criteria | X | | | | | | | | | | | | | | | |
| Brief physical examination, oral examination | X | | | | | | | | | | | | | | | Х |
| Substance testing (drugs, alcohol, tobacco) | Х | | | | | | | | | | | | | |] | |
| Serum pregnancy test in women | Х | | | | | | | | | | | | | | | |
| Admittance to clinic | X | | | | | | | | | | | | | | | |
| Discharge | | | | | | | | | | | | | | | | X1 |
| Training ² | X | | | | | | | | | | | | | | | |
| Haematology, clinical chem and urinalysis (include liver chem)3 | X | | | | | | | Χ | | | | | | | | Χ |
| Exposure to dosing | | Χ | Χ | X | Χ | X | X | X | Χ | X | Χ | X | X | X | Χ | |
| PK blood sample | | X ⁴ | | | | | | X ⁴ | | | | | | | X ⁴ | X |
| Stationary pump air monitoring ⁵ | | Χ | | | | | | Χ | | | | | | | Χ | |

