| 3.27. | Bystander Safety (Part 1, Cohort C) | LB1 | Summary of Haematology Changes from Baseline by Visit – Bystander | Only for Cohort C, Part 1. | SAC | | | |
| 3.28. | Safety | LB17 | Summary of Hematology Values by Potential Clinical Importance – Part 1 | This will not include Cohort C, Part 1. | SAC | | | |
| 3.29. | Safety | LB17 | Summary of Hematology Values by Potential Clinical Importance – Part 2 | | SAC | | | |
| 3.30. | Bystander Safety (Part 1, Cohort C) | LB17 | Summary of Hematology Values by Potential Clinical Importance – Bystander | Only for Cohort C, Part 1. | SAC | | | |

| Safety: | Safety: Tables | | | | | | |
|---------|---|-------------------------|---|---|---------------------------|--|--|
| No. | Population | IDSL / Example Shell | Title | Programming Notes | Deliverable [Priority] | | |
| Labora | tory: Coagulati | on | | | | | |
| 3.31. | Safety | LB1 | Summary of Coagulation Changes from Baseline by Visit – Part 1 | Only for Cohorts B, Part 1. | SAC | | |
| 3.32. | Safety | LB1 | Summary of Coagulation Changes from Baseline by Visit – Part 2 | Only for Cohorts B, Part 2. | SAC | | |
| Teleme | try | | | | | | |
| 3.33. | Safety | Non-standard SAFE_T2 | Summary of Telemetry Findings – Part 1 | This will not include Cohort C, Part 1. | SAC | | |
| 3.34. | Safety | Non-standard SAFE_T2 | Summary of Telemetry Findings – Part 2 | | SAC | | |
| Spirom | etry | | | | | | |
| 3.35. | Safety | Non-standard SAFE_T3 | Summary of Spirometry Data – Part 1 | This will not include Cohort C, Part 1. | SAC | | |
| 3.36. | Safety | Non-standard SAFE_T3 | Summary of Spirometry Data – Part 2 | | SAC | | |
| ECG | | | | | | | |
| 3.37. | Safety | EG1 | Summary of ECG Findings by Visit – Part 1 | This will not include Cohort C, Part 1. | SAC | | |
| 3.38. | Safety | EG1 | Summary of ECG Findings by Visit – Part 2 | | SAC | | |
| 3.39. | Bystander Safety (Part 1, Cohort C) | EG1 | Summary of ECG Findings by Visit – Bystander | Only for Cohort C, Part 1. | SAC | | |
| 3.40. | Safety | EG2 | Summary of Change from Baseline in ECG Values by Visit – Part 1 | This will not include Cohort C, Part 1. | SAC | | |

| Safety: | Tables | | | | |
|----------|---|-------------------------|---|--|---------------------------|
| No. | Population | IDSL / Example Shell | Title | Programming Notes | Deliverable [Priority] |
| 3.41. | Safety | EG2 | Summary of Change from Baseline in ECG Values by Visit – Part 2 | | SAC |

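### Cohort B spirometry taken after BAL is not marked, so in Part 1 a procedure effect on FEV1 or FVC cannot be told apart from a 60 mg BID effect

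*SAP*

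**What the plan says.** All timing is in SAP section 11.2.1, in the repeat-dose schedule that applies to every repeat-dose cohort except Cohort A of Part 1.

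- Spirometry is marked on Days 1, 3, 6, 11 and 14. Day 11 carries note 8: "To be performed at the following timepoints in the mornings only: pre-dose and 4 h post-dose". Day 14 carries note 7: "pre-dose, and 0.25 (in participants with COPD only), 0.5, 1, 4 h post-dose".
- BAL carries note 14: "Done once during these four days, as soon as possible (within 1 h) after the first dose of the day". Its mark is at Day 10.
- Telemetry, scheduled on Day 13, carries note 9: "Telemetry may be performed on Days 11 or 12 instead, not to coincide with the BAL procedure".
- ECG and vital signs carry note 11: "When BAL is performed, vital signs and ECG will be performed before and after the procedure and oxygen saturation will be measured continuously".

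On analysis, section 7.6 says of spirometry: "The maximum of the measurements will be calculated. All measurements will be listed". Section 7 lays summaries out by dose and time, and section 11.4.2 uses planned time relative to dosing. The tables are 3.35 ("Summary of Spirometry Data – Part 1") and 3.36, its Part 2 counterpart. The SAFE_T3 shell has generic time-period rows and one placebo column. SAFE_L1 lists visit date, time of first exhalation and the readings. Neither shell refers to BAL. Section 5.1 defines the Part 1 placebo group as Cohorts A and B together.

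**The concern.** Spirometry is one of the assessments under the primary safety endpoint (section 2.2), the product is inhaled, and lavage acts on the organ that spirometry measures. The schedule recognises that BAL can disturb other assessments: telemetry may be moved off the BAL day, and ECG and vital signs are taken before and after it. Spirometry has neither provision, and the analysis sections do not fill the gap.

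A Day 11 reading a few hours after lavage therefore shares a table row with readings from participants not yet lavaged. The late readings bear most directly on repeat-dose tolerability. If FEV1 or FVC fell there, a reader of Table 3.35 could not tell procedure from dose. A fall caused by the procedure could be read as drug effect, or a drug effect dismissed as procedure.

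**Working it through.** The SAP has no figure of its own to reproduce here. The check is one of timing.

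**Window.** Note 14 gives four days and the mark is at Day 10, which suggests Days 10–13. Note 9 fits: Day 13 telemetry needs moving only if BAL can fall on Day 13.

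**Interval from BAL to spirometry** = 24 × (spirometry day − BAL day) + spirometry hour − BAL delay. The delay is 0 to 1 h after the morning dose (note 14). Morning doses are taken as 24 h apart and the length of the procedure is ignored.

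| BAL day | Day 11 pre-dose | Day 11, 4 h | Day 14, pre-dose to 4 h |
|---|---|---|---|
| 10 | 23–24 h after | 27–28 h after | 95–100 h after |
| 11 | before BAL | 3–4 h after | 71–76 h after |
| 12 | before BAL | before BAL | 47–52 h after |
| 13 | before BAL | before BAL | 23–28 h after |

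Example: BAL on Day 11, 4 h reading: 24 × 0 + 4 − (0 to 1) = 3 to 4 h.

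The Day 11 4 h reading follows BAL on 2 of 4 permitted days, the Day 11 pre-dose reading on 1 of 4, and Day 14 readings on 4 of 4.

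**Comparison groups, Part 1.** Cohort A's schedule has no BAL row. Its spirometry during 30 mg BID falls on study Days 6, 8, 11, 16 and 19. With the first BID dose on Day 6, subtracting 5 gives repeat-dose Days 1, 3, 6, 11 and 14, the same days as Cohort B. At repeat-dose Day 14, every 30 mg BID reading is free of BAL and every reading from a lavaged 60 mg BID participant follows it.

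For pooled placebo, row alignment matters, and SAFE_T3 does not fix it. By study day, Cohort A placebo enters the Day 11 row but has no Day 14 spirometry. By repeat-dose day, it enters both rows.

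**Comparison groups, Part 2.** The single-dose treatment schedule ends at Day 2, so Day 11 and Day 14 placebo readings come only from Cohort B, which shares the BAL schedule.

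**How an effect would pass through.** Let *d* be the fall in affected readings (not given in the SAP), *p* the fraction of 60 mg BID readings in a row that are affected, and *q* the share of placebo readings in that row that come from Cohort A (split not given). Assume Cohort B placebo is lavaged on the same pattern. The distortion is:

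- against 30 mg BID: *p* × *d*
- against pooled placebo: *p* × *d* − (1 − *q*) × *p* × *d* = *q* × *p* × *d*
- against Cohort B placebo: *p* × *d* − *p* × *d* = 0

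If BAL days are spread evenly (assumption) and only same-day readings are affected, *p* = 1/4 for the Day 11 4 h row. Each point of *d* then moves the 60 mg BID mean by 0.25 point. If next-day readings are equally affected, *p* = 2/4 and the shift is 0.5 point.

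**The case against.** A reader might infer that any lavage effect is tabulated as a 60 mg BID effect. The SAP does not support that. One schedule with one BAL row covers active and placebo participants, and it exempts no placebo participant. A lavage effect would therefore also appear in Cohort B placebo, and Part 2 would be balanced.

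A reader might also infer that no late 60 mg BID reading is free of the procedure. That is not so: with BAL on Day 12 or 13 both Day 11 readings precede it, and with BAL on Day 11 the pre-dose reading does. Days 1, 3 and 6 are all before BAL.

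Nor is the contrast with telemetry as sharp as it looks. Note 9 stops telemetry from coinciding with BAL, not from following it, and the move is optional. By that standard only BAL on Day 11 is a comparable lapse; under a Days 10–13 window, Day 14 spirometry never shares a day with BAL.

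Further, no hypotheses are tested (section 2.4), Table 3 plans no change from baseline for spirometry, pooling of placebo is optional (section 7), and all readings are listed. The window is inferred from a merged cell, and in the next row the urea mark appears under Day −1 although note 15 ties it to bronchoscopy, so column positions are not fully reliable.

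These points limit the concern but do not remove it. In a descriptive study, reading the tables is the safety assessment, and neither tables nor listing show which readings follow BAL. Shifting the window by a day changes the count of permitted days on which the Day 11 4 h reading follows BAL (3 of 4 for Days 9–12, 1 of 4 for Days 11–14), not the gap. The timing may belong to the protocol, but how the resulting readings are classified is a matter for the SAP.

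**Conclusion.** The point holds in limited form. In Cohort B of each part, Day 11 spirometry can follow BAL, and Day 14 spirometry does so in every lavaged participant. Section 7.6, Tables 3.35–3.36 and SAFE_L1 do not mark these readings. In Part 1, comparison with 30 mg BID mixes procedure and dose, and so does comparison with pooled placebo wherever Cohort A contributes to the row. In Part 2 the active–placebo comparison is balanced, but the readings are still unmarked.

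This rests on the Days 10–13 reading of the window and, for the balance in Part 2, on placebo participants being lavaged. The SAP gives no size for a lavage effect, so the size of any distortion is unknown. The point calls for a cheap improvement to the analysis and does not show that the planned tables will mislead.

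**What to change.** In section 7.6, add a rule that Cohort B spirometry in each part is classified as before or after BAL from actual times. Then:

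- add hours since BAL to SAFE_L1;
- in Tables 3.35–3.36, split or footnote Day 11 by BAL status and label Day 14 as post-BAL;
- in Table 3.35, show Cohort B placebo separately as the comparator at the Day 11 and Day 14 timepoints, rather than only the pooled Cohort A and B column, and state whether rows follow study day or repeat-dose day.

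Keep all Day 14 readings in the summaries, and do not restrict the 60 mg BID statement to before-BAL readings: that would discard all end-of-treatment spirometry from lavaged participants.

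The cost is a few sentences, some table rows or footnotes, one placebo column and one listing column. Time of first exhalation is already listed; the rule assumes that the BAL time is recorded too. The schedule does not change. The downside is small numbers in each Day 11 row and in Cohort B placebo, so those rows should be read as description only.

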11.3. Appendix 3: Study Phases and Treatment Emergent Adverse Events

11.3.1. Study Phases

Assessments and events will be classified according to the time of occurrence relative to dosing.

| Study Phase | Definition |
|----------------|---|
| Pre-Treatment | Date ≤ Study Treatment Start Date |
| On-Treatment | Study Treatment Start Date < Date ≤ Study Treatment Stop Date |
| Post-Treatment | Date > Study Treatment Stop Date |

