5.1. Study Treatment & Sub-group Display Descriptors

| | Treatment Group Descriptions | | | | | | | |
|--|-------------------------------------|----------------------------|---|-----------|--|--|--|--|
| RandAll NG Data Displays for Reporting | | | | | | | | |
| Code | Description | Display Header | Footnote Treatment Description | Order [1] | | | | |
| S1 | CCI15106-IP 60 mg – Single Dose | CCI15106 SD 60mg(HV) | CCI15106-IP 60 mg Single Dose for Part 1, Cohort A | 1 | | | | |
| S2 | CCI15106-IP 120 mg – Single Dose | CCI15106 SD 120mg(HV) | CCI15106-IP 120 mg Single Dose for Part 1, Cohort A | 2 | | | | |
| R1 | CCI15106-IP 30 mg - BID | CCI15106 BID 30mg(HV) | CCI15106-IP 30 mg BID for Part 1, Cohort A | 3 | | | | |
| R2 | CCI15106-IP 60 mg - BID | CCI15106 BID 60mg(HV) | CCI15106-IP 60 mg BID For Part 1, Cohort B | 4 | | | | |
| Р | Placebo | Placebo(HV) | Placebo for Part 1 Cohorts A and B | 5 | | | | |
| S1 | CCI15106-IP 60 mg – Single Dose | CCI15106 SD 60mg(COPD) | CCI15106-IP 60 mg Single Dose for Part 2, Cohort A COPD | 6 | | | | |
| R2 | CCI15106-IP 60 mg - BID | CCI15106 BID 60mg(COPD) | CCI15106-IP 60 mg BID for Part 2, Cohort B COPD | 7 | | | | |
| Р | Placebo | Placebo(COPD) | Placebo for Single Dose and BID for COPD | 8 | | | | |
| BYS | Bystander Cohort | Bystander | Bystander | 9 | | | | |

NOTES:

1. Order represents treatments being presented in TFL, as appropriate.

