- Summary = Represents TFL related to any summaries (i.e. descriptive statistics) of the observed raw data.
- Individual = Represents FL related to any displays of individual participant observed raw data.
- 1. Listings will include participant's numbers for individual AE's & AE system organ classes, preferred terms and verbatim text.
- 2. Chemistry summaries will include both changes from baseline & emergent results by PCI criteria.
- 3. Listings and summaries for ECGs and vital signs include treatment emergent PCI results

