- 10. PK samples on days 1, 3, 6, and 19 will be collected at the following timepoints: pre-dose, 0.25, 0.5, 0.75, 1, 2, 4, 6, 8, 10, 12 h. On day 2, one sample in the morning (24h post day 1 dose). On days 4 and 5, one sample on each morning (24h and 48h post day 3 dose). On days 6 and 19, the evening dose will be given after 12 h post-dose sample is collected. On all other days, PK sample will be collected once, before the morning dose (if on dosing days).

Schedule for Cohort A Part 2 (and all other single dose administrations)

| | Treatment Period, Days (D) and hours (h) | | | | | | | | | | | | | |
|---|--|---|----|-------|------|-------|----|----|----|----|----|-----|-----|-----------------|
| | D-1 D1 | | | | | | | | | | | | | D2 |
| Procedure | | Pre- dose | 0h | 0.25h | 0.5h | 0.75h | 1h | 2h | 4h | 6h | 8h | 10h | 12h | 24h |
| Inclusion and exclusion criteria | Х | | | | | | | | | | | | | |
| Brief physical examination, oral examination | X | | | | | | | | | | | | | Х |
| Substance testing (drugs, alcohol) | X | | | | | | | | | | | | | |
| Serum pregnancy test in women | X | | | | | | | | | | | | | |
| Admittance to clinic | X | | | | | | | | | | | | | |
| Inhaler device training ¹ | Х | | | | | | | | | | | | | |
| Randomization | Х2 | | | | | | | | | | | | | |
| Discharge | | | | | | | | | | | | | | Х3 |
| Haematology, clinical chem and urinalysis (include liver chem)4 | X | | | | | | | | | | | | | Χ |
| Spirometry | | X5 | | X6 | Χ | | Χ6 | | X6 | | | | | |
| Telemetry | | 30 min pre-dose and continuous until at least 4 h | | | | | | | | | | | | |
| 12-lead ECG and vital signs | | XXX | | X | | | Χ | X | X | | Χ | | Χ | |
| CCI15106-IP or placebo treatment | | | Х | | | | | | | | | | | |
| PK blood sample ⁷ | | Х | | Х | X | X | Х | Х | Х | Χ | Х | Х | X | Х |
| AE review | ← | | | | | | | | | | | | | |
| SAE review | (| | | | | | | | | | | | | |
| Concomitant medication review | (====== | | | | | | | | | | | | | > |

- 1. Day -1 inhaler training may be done on Day 1 instead, before the first dose administration. Other time-points may be added per investigators discretion
- 2. Can be performed on Day 1 prior to dosing
- 3. After all assessments are completed
- 4. To be drawn fasting (for at least 8 h)
- 5. To be performed within 15 to 60 minutes pre-dose
- 6. To be performed after ECG, VS and PK blood draw are obtained
- 7. Additional PK collection time points may be added to better characterize the PK profile

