11.3.2. Treatment States for Adverse Events Data

| Treatment State | Definition |
|-----------------|--|
| Pre-Treatment | AE Start Date < Study Treatment Start Date if AE start time not available; else |
| Pre-mealment | AE Start Date time < Study Treatment Start Date time |
| On-Treatment | If AE onset date is on or after treatment start date & on or before treatment stop date. |
| | Study Treatment Start Date ≤ AE Start Date ≤ Study Treatment Stop Date |
| Post-Treatment | If AE onset date is after the treatment stop date. |
| | AE Start Date > Study Treatment Stop Date |
| Onset Time | If Treatment Start Date > AE Onset Date = AE Onset Date - Treatment Start Date |
| Since 1st Dose | If Treatment Start Date ≤ AE Onset Date = AE Onset Date - Treatment Start Date +1 |
| (Days) | Missing otherwise. |
| Duration (Days) | AE Resolution Date – AE Onset Date + 1 |
| Drug-related | If relationship is marked 'YES' on CRF OR value is missing. |

NOTES:

• If the study treatment stop date is missing then the AE will be considered to be On-Treatment.

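### The SAP's study-phase table (11.3.1) puts the whole first dosing day in Pre-Treatment, so a single-dose cohort has no On-Treatment assessments, and it conflicts with the adverse-event rule in 11.3.2

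*SAP*

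**What the plan says.** SAP section 11.3.1 opens by stating its purpose: "Assessments and events will be classified according to the time of occurrence relative to dosing". Its table then works on dates alone:

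- A reading counts as Pre-Treatment when "Date ≤ Study Treatment Start Date" holds, so the start day is included.
- It counts as On-Treatment when "Study Treatment Start Date < Date ≤ Study Treatment Stop Date" holds, so the start day is left out.
- Anything dated later than the stop date is Post-Treatment.

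Section 11.3.2 has a separate rule for adverse events. On-Treatment there is "Study Treatment Start Date ≤ AE Start Date ≤ Study Treatment Stop Date", and its Pre-Treatment row compares date and time when an onset time is available. Medications have their own definition in 11.3.1.1. Nothing else in the SAP assigns a phase to ECG, vital signs, spirometry, telemetry or laboratory data.

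Note 3 under Table 3 (section 7) says: "Listings and summaries for ECGs and vital signs include treatment emergent PCI results". It does not say which rule makes such a result treatment-emergent.

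**The concern.** The two tables place the equality on opposite sides of the treatment start date. In 11.3.1 the start day belongs to Pre-Treatment; in 11.3.2 it belongs to On-Treatment. Because 11.3.1 covers events as well as assessments, an adverse event that begins after dosing on Day 1 is Pre-Treatment under one table and On-Treatment under the other.

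The hours after an inhaled dose are when acute effects are looked for, and ECG, telemetry, spirometry and vital signs are among the primary safety endpoints (section 2.2). A programmer who builds a treatment-emergent flag for ECG or vital signs from the only phase rule the SAP gives for such data would exclude every Day 1 post-dose reading. In a cohort dosed once, that leaves no post-dose reading from the dosing day.

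**Working it through.** The plan gives no figure to reproduce. The check is to apply the rule to the schedules.

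**Inputs**

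- Rule 11.3.1, with d = date, s = start date, e = stop date: Pre if d ≤ s; On if s < d ≤ e; Post if d > e.
- Boundary of 11.3.2, by date: Pre if d < s; On if s ≤ d ≤ e; Post if d > e.
- Part 2 Cohort A (section 5.1): "CCI15106-IP 60 mg Single Dose for Part 2, Cohort A COPD". One dose on Day 1, so s = e = Day 1. The SAP does not state this equality; it follows from the single dose.
- Single-dose schedule (11.2.1), after dosing on Day 1: ECG and vital signs at 0.25, 1, 2, 4, 8 and 12 h (6 time points); spirometry at 0.25, 0.5, 1 and 4 h (4 time points). Laboratory tests follow on Day 2.
- Cohorts B are dosed on Days 1 to 14. Part 1 Cohort A has its first dose on Day 1 and its last on Day 19.

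**Part 2 Cohort A.** With s = e, the On condition becomes Day 1 < d ≤ Day 1, which no date satisfies.

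| Post-dose data | 11.3.1 by date | 11.3.1 with Date read as date-time | 11.3.2 boundary |
|---|---|---|---|
| ECG/vital signs, 6 time points | 6 Pre | 6 Post | 6 On |
| Spirometry, 4 time points | 4 Pre | 4 Post | 4 On |
| Day 2 laboratory tests | Post | Post | Post |

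The middle column matters. Reading Date as date-time does not rescue the rule: a single dose has the same start and stop time, so On-Treatment stays empty and the readings move to Post-Treatment instead.

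**On-Treatment days by cohort**

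| Cohort | 11.3.1 | 11.3.2 boundary |
|---|---|---|
| Part 2 A | none | Day 1 |
| Cohorts B, both parts | Days 2–14 | Days 1–14 |
| Part 1 A (overall start and stop) | Days 2–19 | Days 1–19 |

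So the Day 1 post-dose readings of Cohorts B (ECG and vital signs at 2 h, plus post-dose spirometry) and those after the first 60 mg dose in Part 1 Cohort A are also Pre-Treatment under 11.3.1.

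**Which displays depend on the phase table**

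- Baseline (5.2.1) is the last assessment before dosing, displayed as Day 1 pre-dose for ECG, vital signs, spirometry and telemetry and as Day -1 for laboratory tests. It makes no use of phase.
- Summaries and analyses run on planned time relative to dosing (11.4.2), so by-time-point tables are unaffected. PK analyses do not use phase either.
- Section 7.2 sends the reader to Appendix 3 for AE treatment states, which is the 11.3.2 table.
- The treatment-emergent PCI results in note 3 of Table 3 need a definition of treatment emergence, and 11.3.1 is the only one available for assessments.

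**The case against.** The strongest reply is that no display is shown to lose data. Note 3 of Table 3 does not cite 11.3.1. The ECG PCI shells in 11.11 have rows for the worst post-baseline value, and 11.5.1 describes a row for any visit after baseline that also applies to relevant PCI tables. With the baseline of 5.2.1, Day 1 post-dose readings are post-baseline and would be counted. No table title, programming note or shell asks for Pre-, On- or Post-Treatment phase on ECG, vital signs, spirometry or telemetry. This stands as a limit on the consequence: the 6 and 4 time points are mislabelled readings, not demonstrated omissions. It does not defend the rule, and the SAP never says that treatment-emergent means post-baseline.

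Two stronger readings are tempting, and the document supports neither:

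- A reader might infer that a Day 1 post-dose value could become baseline because it is labelled Pre-Treatment. Section 5.2.1 ties baseline to dosing, not to phase, and 5.2.2 says those definitions apply unless otherwise specified.
- A reader might infer that Part 2 Cohort A has no on-treatment data at all. Under 11.3.2, a Day 1 post-dose adverse event there is On-Treatment. The empty category concerns assessments under 11.3.1.

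**Conclusion.** The rule in 11.3.1 is wrong as written. It defeats its own stated purpose, conflicts with 11.3.2 for a post-dose adverse event on Day 1, and gives no On-Treatment category when treatment starts and stops on the same day. Per participant in Part 2 Cohort A, 6 of 6 Day 1 post-dose ECG/vital-sign time points and 4 of 4 spirometry time points are Pre-Treatment.

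The exposure is narrow: only flags or displays that derive treatment emergence from 11.3.1, most plausibly the ECG and vital-sign PCI results. Whether any such display would lose readings depends on how the flag is programmed, which the SAP leaves open.

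The conclusion assumes that the table is applied literally, that start date equals stop date for the single-dose cohort, and that the 12 h reading falls on the calendar date of dosing, as the schedule's Day 1 column implies.

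**What to change.** Replace the three definitions in 11.3.1 so that they agree with 11.3.2:

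- Pre-Treatment: date-time before the first dose date-time. If the clock time is missing, use the planned time point relative to dose.
- On-Treatment: from the first dose date-time through the treatment stop date, inclusive. This is the end-point 11.3.2 already uses, and it is not empty for a single dose.
- Post-Treatment: date after the treatment stop date.

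Date-time is needed at the start boundary because a date-only rule that includes the start day would label the Day 1 pre-dose assessments On-Treatment. The Day 2 laboratory tests in Part 2 Cohort A remain Post-Treatment, as they are now.

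Add one sentence to note 3 of Table 3 or to Appendix 7 saying that treatment-emergent PCI flags use this definition, so that Day 1 post-dose values are counted.

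The cost is three table cells and one sentence, made before phase flags are programmed. Listings already carry planned and actual time relative to dosing (11.4.2), so no new data are needed.
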